2.4. Participant timeline

Examples of potential participants' timeline are described in table 1.

Table 1. Participants' timeline														
	Year	2019						2020						
	Stage	Jul	Aug	Sep	Oct	Nov	Dec	Jan	Feb	Mar	Apr	May	Jun	Jul
	Baseline participant recruitment													
Child n°1	Baseline assessment	■												
	3-month follow-up				■									
	6-month follow-up							■						
Child n°2	Baseline assessment			■										
	3-month follow-up						■							
	6-month follow-up								■					
Child n°3	Baseline assessment					■								
	3-month follow-up							■						
	6-month follow-up										■			
Child n°4	Baseline assessment					■								
	3-month follow-up						■							
	6-month follow-up										■			
Child n°5	Baseline assessment						■							
	3-month follow-up							■						
	6-month follow-up								■			■		
Child n°6	Baseline assessment							■						
	3-month follow-up								■					
	6-month follow-up											■		

2.5. Sample size

The sample size for the development of the Pediatric Pain Screening Tool included 321 children aged 8-18 years old ²⁸. A minimum of 100 subjects is required for a stable variance-covariance matrix ⁴⁵, and following the rule of thumb of at least 10 events for variable (or items within the prognostic tool) ⁴⁵, around 300 individuals would be necessary for a maximum of 30 items included in the tool. However, in case of presence of binary predictors with low prevalence, ≥ 20 events per variable would be necessary ⁴⁶ (this would consequently lower the number of items that it is possible to include in the prognostic tool).

Previous studies have shown an annual consultation prevalence of 104 - 200 per 10,000 registered persons in children aged 3 to 19 years old ^{24,25,47}. Here below, different potential scenarios about participants' recruitment are described. These scenarios are calculated on a conservative estimate of 30% study participation rate. This is a worst-case scenario, and this approach is taken in order to have a safe recruitment that will provide us with enough children and adolescents for the development of the tool.

Based on the prevalence estimate of 119 ²⁴ per 10,000 registered persons (which is a likely prevalence for children aged 8-19), at least 168 general practices of a medium size of 5000 individuals each will be needed to recruit at least 300 participants at baseline (provided that 30% of all children aged 8-19 with a consultation for knee pain during a period of 6 month decide to take part in the study). This means that the overall target population includes 840.000 persons (168*5000) registered in general practices, which corresponds to 1/7 of the whole Danish population. Indeed, among these 840.000 persons, approximately 168.000 (20%) will be aged between 8 and 19 years old and 1,999 (119 per 10,000 registered persons) of these young people will have a consultation for knee pain in one year. Of these, 999 will have a consultation in a 6-

month period (which is the duration of the baseline recruitment). If 30% of these children decide to take part in the study, there will be data on 300 children aged 8-19 at baseline. However, for the development of the START-BACK screening tool 244 patients were identified, of which only 131 (54%) returned the baseline questionnaire and 107 (82%) agreed to further contact ²⁹. Therefore, if we aimed at only 100 children aged 8-19 years old with a consultation for knee pain in a 6-month period and by keeping the same proportions shown above (i.e. only 30% baseline participation rate), only 56 general practices of a medium size of 5000 individuals each would be needed (corresponding to a target population of 280.000 individuals, of which 56.000 aged 8-19 years old). A target of 100 children would enable approximately 30 individuals in each prognostic risk group (low/medium/high).

Conversely, based on the highest prevalence estimate (200 per 10,000 registered persons) and considering a 30% participation rate into the study, 33 general practices of a medium size of 5000 individuals each would be needed (corresponding to a target population of 165.000 individuals, of which 33.000 aged 8-19 years old) to recruit at least 100 children. To recruit at least 300 children, 100 general practices of a medium size of 5000 individuals each would be needed (corresponding to a target population of 500.000 individuals, of which 100.000 aged 8-19 years old). Alternatively, it might be possible to target fewer bigger general practices (e.g. 18 general practices of a medium size of 10.000 individuals to recruit 100 children).

In addition, if only 100 children will be recruited from general practices, it might be possible to perform an extra recruitment through social media that would complement the group of children recruited through general practices, in order to achieve a total sample size of at least 300 children. In this case, sensitivity analysis would be performed to check for any potential difference in characteristics between the sample recruited through general practices and social media.

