2.3. Outcome measures

The primary outcome measure will be the recurrence/persistence of activity-limiting knee pain (i.e. yes/no pain that is limiting activities in the same knee) at 3-month follow-up⁴². Participants will also be asked about continuity of their knee pain (i.e. “how long have you been free of knee pain?”), to enable the distinction between recurrence (on/off knee pain episodes between baseline and follow-up) and persistence (continuous knee pain from baseline to follow-up) of knee pain. A secondary outcome measure that will be collected is the recurrence/persistence of activity-limiting knee pain at 6-month follow-up.

Previous studies have shown an effect of the treatment received on the change in risk group for the recurrence/persistence of pediatric pain⁴³ and on the change in pain and function⁴⁴. Therefore, an additional outcome measure that might potentially be assessed include the treatment effectiveness on the recurrence/persistence of knee pain (provided that there will be the possibility to collect data on the treatment given). For practical reasons, it might be considered assessing this additional outcome on a subsample of children and adolescents.

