2.6. Development of the tool

Clinically meaningful prognostic factors for knee pain in children and adolescents were identified from a review of the current literature on the topic. Initially, the most important domains for the prognosis of knee pain and the specific items to be included in the tool were selected based on the strength of association from previous studies identified within the literature and from meta-analysis of individual participant data. Additional factors were included after discussion with general practitioners that agreed to take part to the study and staff working at the Center for General Practice at Aalborg University. During this stage, great emphasis was given to include only the most necessary factors taking in mind that the prognostic tool should be used in a reasonable time of a consultation within general practice.

Items relative to the specific prognostic factors were initially selected from validated scales where possible (e.g. regarding pain characteristics, limitation in daily activities, sport participation, psychological factors). When multiple items within a scale or multiple scales were available for a prognostic factor, the relevant literature on the topic was identified and discussed at meetings with general practitioners and staff working at the Center of General Practice at Aalborg University in order to select the most appropriate items within the possible options. Following previous tools developed for pain in children and adolescents^{28,48,49}, items were properly worded for the age and properly framed with respect to the response options (e.g. direction, time intervals, avoiding double-barreled items).

The initial version of the tool was tested and implemented during the pilot stage (great emphasis was given to the cognitive interviews that were carried out with children and adolescents), until reaching a final version that will be used for the collection of the data, as further described below in section 2.8.6. The outline of the final tool is provided in the figure below:

Knæ project

Disse spørgsmål handler om dine knæsmerter. Sæt kryds i den boks som bedst beskriver hvordan du har det, eller skriv i tekstdokumentet. Hvis du er i tvivl, så bedes du svare så godt du kan. Spørgsmålene står i venstre side, og svarmulighederne i højre side af skemaet.

Navn	
1. Hvor gammel er du?	(_____)
2. Er du en pige eller en dreng?	 Pige  Dreng

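### Section 2.5 states its rule in events but counts children: 300 children support 30 items only if every child has the outcome, and 15 items at an assumed 50% event rate

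*Combined protocol and SAP*

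**What the plan says.** Section 2.5 introduces the rule with the words "following the rule of thumb of at least 10 events for variable (or items within the prognostic tool" and ends the same sentence with "around 300 individuals would be necessary for a maximum of 30 items included in the tool". The next sentence adds a stricter condition, "in case of presence of binary predictors with low prevalence, ≥ 20 events per variable would be necessary", and notes that this would reduce the number of items.

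The 300 is an enrolment figure: the main recruitment scenario in Section 2.5 ends with "there will be data on 300 children aged 8-19 at baseline". If general practices supply only 100 children, "it might be possible to perform an extra recruitment through social media that would complement the group of children recruited through general practices", to bring the total to at least 300.

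The primary outcome in Section 2.3 is binary, "yes/no pain that is limiting activities in the same knee", assessed at 3 months. Step 3 of Section 2.10 fits a multiple logistic regression and reports an odds ratio for each item. Section 2.6 shows the instrument ("The outline of the final tool is provided in the figure below"), which has 13 numbered questions. No section gives an expected 3-month event rate, an expected number of events or a count of model parameters.

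**The concern.** An events-per-variable rule limits the number of predictors by the number of participants who have the outcome. Section 2.5 applies its multiplier to the number of participants enrolled. The stated maximum of 30 items is therefore too high at any event rate below 100%, and at 100% no logistic model could be fitted.

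The regression in step 3 of Section 2.10 is meant to inform the item scores. The risk groups, the ROC cut-offs and the reported sensitivity and specificity then follow from the overall score. With too few events per parameter the weights are unstable, and performance measured in the same children looks better than it is. The text of Section 2.10 names neither shrinkage nor internal validation to offset this. A reader of Section 2.5 would conclude that a tool of about 15 items has twice the data it needs. Whether that is true depends on an event rate the plan does not state.

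**Working it through.** **Inputs.** From Section 2.5: 10 events per variable (20 where binary predictors have low prevalence), 300 children at baseline, 30 items, fallback of 100 children. From Section 2.6: the tool. The event rate *p* is not given. The nearest figure is in Section 1.1, where about half of adolescents still report knee pain after 1 or 2 years. That is a different outcome and time point, so 50% is used only as an assumption, with a range of 30% to 70%.

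**The plan's own figure.** 10 × 30 = 300. This equals the number of children only if *p* = 1.

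**The rule as worded.** Events = 300 × *p*; parameters supported = events / 10 or events / 20, rounded down; children needed for 30 items = 300 / *p*. The plan does not say whether it means events or the smaller outcome class, so the smaller-class count, min(*p*, 1 − *p*) × 300 / 10, is shown separately.

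| Event rate (assumed) | Events in 300 | Parameters at 10 (20) | Smaller class, at 10 (20) | Events per item if 30 items | Children for 30 items at 10 events each |
|---|---|---|---|---|---|
| 30% | 90 | 9 (4) | 9 (4) | 3 | 1000 |
| 50% | 150 | 15 (7) | 15 (7) | 5 | 600 |
| 60% | 180 | 18 (9) | 12 (6) | 6 | 500 |
| 70% | 210 | 21 (10) | 9 (4) | 7 | 429 |

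The 30-item maximum overstates capacity by 1/*p*: 3.3-fold at 30%, twofold at 50%, 1.4-fold at 70%. On the smaller-class count, 15 is the ceiling at any event rate.

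**Loss to follow-up (assumed 10/20/30%).** Children with an outcome: 270/240/210. At 50% this gives 135/120/105 events, hence 13/12/10 parameters. As an illustration only, Section 2.5 reports for another study that "107 (82%) agreed to further contact" out of 131. Then 300 × 107/131 = 245 children and 122.5 events at 50%, which supports 12 parameters.

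**The tool.** Questions 9 and 10 each contain two items, so the 13 questions give about 15 scorable items, leaving out free-text sport type and the individual pain-site ticks. At 10 events each, 15 items need 150 events. The event rate required is 150/300 = 50% with complete follow-up, and 150/270 = 56%, 150/240 = 63% or 150/210 = 71% after 10/20/30% loss. With 245 children it is 150/245 = 61%.

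The coding of multi-category answers is not specified. Entered as categories, the parameters are 1+1+2+3+1+4+1+4+4+4+1+1+7+1+4 = 39, which is 150/39 = 3.8 events each at 50%. If the yes/no smoking item has low prevalence (none is given) and the 20-event rule is applied to the whole tool, 15 × 20 = 300 events are needed, that is, every child.

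**The fallback.** 100 children support 100 × 0.5 / 10 = 5 parameters at 50% and 7 at 70%. Fifteen items fail at any rate, since 100/15 = 6.7 events each even if every child had the outcome.

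**The case against.** The strongest defence is that little follows from the slip. Thirty is a ceiling and not a plan. At 50% with complete follow-up the roughly 15-item tool meets the 10-event rule, and Section 2.10 leaves room to drop items. This stands, and it limits the severity. It does not make the stated ceiling right, and it holds only at one favourable combination of event rate and follow-up.

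The 50% is also weak: it concerns any knee pain at 1 to 2 years, not activity-limiting pain in the same knee at 3 months among children who consult. That stands too, which is why a range is shown. The conclusion does not need it, because 300 × *p* / 10 is below 30 for every *p* below 1.

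Recruitment may beat the plan. Section 2.5 calls 30% participation a worst case and quotes 54% questionnaire return elsewhere. Applied to the 999 expected consultations, 54% gives about 540 children. That is a real margin for enrolment, but it does not change what 300 children support, and 540 × 0.5 / 10 = 27 is still below 30. Agreement to further contact is likewise only a proxy for retention. Multiple imputation (Section 2.11) adds no observed events.

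The 20-event sentence shows that the authors did not treat 30 as firm. It changes the multiplier and leaves the conversion from children to events undone. Applying it to all 15 items is one reading; applied to the smoking item alone it needs 14 × 10 + 20 = 160 events.

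Finally, the 10-per-variable rule is cited to a paper on measurement properties of questionnaires, so the slip may lie in the word events. The documents cannot settle this. On either reading, the capacity of the planned logistic model in events is unstated.

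The smaller-class count, the 39-parameter coding and the 100-child case are side points. The plan does not claim that 100 children satisfy this rule.

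**Conclusion.** The concern holds. The maximum of 30 items for 300 children equates children with events and is wrong at any event rate below 100%. At an assumed 50% and with no loss, the capacity is 15 parameters at 10 events each, half the stated figure. Across 30% to 70% it is 9 to 21 counting events, or 9 to 15 counting the smaller outcome class. With 10% to 30% loss at 50% it falls to 13 to 10.

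The correction should be made, but the consequence is modest. The tool is about half the stated maximum, so the error has not produced a 30-item model. What disappears is the apparent margin: 15 single-term items just meet the rule at 50% with complete follow-up, and fail it if the event rate is lower, follow-up is incomplete or items are entered as categories. The event rates and loss rates are assumptions; the gap between children and events is not.

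**What to change.** Restate the capacity in Section 2.5 in events. For example: *No 3-month event rate is available. If 300 children provide a 3-month outcome and 50% have the event (assumed), there are 150 events, supporting 15 model parameters at 10 events per variable and 7 at 20. For event rates of 30% to 70% the capacity at 10 events per variable is 9 to 21 counting events, or 9 to 15 counting the smaller outcome class.*

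Then:
- say which of the two counts is used;
- add the expected number followed up and the capacity after that loss (13/12/10 at 50% for 10/20/30% loss);
- replace the 30-item maximum with the resulting figure;
- state how many parameters the tool uses under the chosen coding, and compare that number with the capacity;
- add that 100 children without the social-media top-up do not meet the rule for deriving weights for the full tool.

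The cost is wording in one section and one parameter count; the restatement itself needs no extra patients. The stated capacity becomes less favourable, and if the parameter count exceeds it the protocol must say so or say how items will be reduced.

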2.11. Full analysis set

In order to obtain a “full analysis set” for the project, participants will have to provide data from baseline through the 3-month and 6-month follow-up, which will allow to estimate the short-term and long-term knee pain prognosis. Please refer to figure 4 for a description of the full analysis set. Data completeness (i.e. completion and accuracy of data forms) will be monitored and actions will be taken to overcome potential problems such as missing data ⁵¹. In case of missing data, the missing observation will be replaced by means of an imputation process (e.g. multiple imputation by chained equation) depending on the number of missing observations for the follow-up stages (i.e. multiple imputation is usually performed when the percentage of missing data is low). A sensitivity analysis will also be carried out in order to compare results between the analysis carried out on the dataset with missing observation (complete-case analysis) and the multiple imputed dataset (multiple imputation analysis). A backup copying of the dataset will be performed daily.

Figure 4. Complete-case and multiple imputed data

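### Section 2.5 counts its targets of 300 and 100 children at baseline with no allowance for later loss, so the number with an outcome is unstated and will be smaller

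*Combined protocol and SAP*

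**What the plan says.** Section 2.5 derives its main target from a rule of at least 10 events per variable and concludes that "around 300 individuals would be necessary for a maximum of 30 items included in the tool". Separately it states that "A minimum of 100 subjects is required for a stable variance-covariance matrix".

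It then solves for the number of practices. At 119 consultations per 10,000 a year, 168 practices of 5000 people "will be needed to recruit at least 300 participants at baseline", and the paragraph ends: "If 30% of these children decide to take part in the study, there will be data on 300 children aged 8-19 at baseline". The fallback ("if we aimed at only 100 children aged 8-19 years old with a consultation for knee pain in a 6-month period") uses the same steps, with "only 30% baseline participation rate" as the only reduction, and needs 56 practices. At 200 per 10,000 the counts are 100 and 33 practices. The section calls the 30% a worst case, chosen so that recruitment is safe, and says that 100 children would give about 30 per risk group.

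The outcomes come later. The primary outcome is activity-limiting knee pain at 3 months and the secondary outcome is the same at 6 months (Sections 2.3 and 2.8.2). For the full analysis set, "participants will have to provide data from baseline through the 3-month and 6-month follow-up" (Section 2.11).

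Loss is expected. Section 1.4 lists it among the things to be assessed (objective 4d), Section 2.7.3 offers a second cinema ticket on completing follow-up, Section 2.8.2 plans two reminders, Section 2.8.3 records reasons for loss, and Section 2.13 allows withdrawal at any time. No section gives an expected rate.

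**The concern.** The requirement and the supply are counted at different times. An events-per-variable rule can be met only by children whose outcome has been observed. The same holds for the logistic regression, ROC curves, cut-off scores, sensitivity, specificity and likelihood ratios in Section 2.10, steps 3 to 6. A child seen only at baseline adds no observed outcome to any of them.

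A reader of Section 2.5 would take 300, or 100 with about 30 per risk group, as the number from which accuracy will be estimated, and would take the worst-case label to cover all sources of shortfall. It covers consent at baseline only. At stake is the honesty of the stated precision, especially in the 100-child scenario, where the risk groups are already small.

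**Working it through.** **Inputs from Section 2.5:** practice size 5000; share aged 8 to 19, 20%; annual consultations 119 or 200 per 10,000; recruitment over half a year; participation 30%.

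**Step 1: reproduce the plan's figures.** Baseline children = practices × list size × 0.20 × annual rate × 0.5 × 0.30.

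- 168 × 5000 × 0.20 × 0.0119 × 0.5 × 0.30 = 299.88 (stated: 300)
- 56 × 5000 × 0.20 × 0.0119 × 0.5 × 0.30 = 99.96 (stated: 100)
- 100 × 5000 × 0.20 × 0.0200 × 0.5 × 0.30 = 300.0 (stated: 300)
- 33 × 5000 × 0.20 × 0.0200 × 0.5 × 0.30 = 99.0 (stated: 100)

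All four agree within rounding, with no term for loss. The arithmetic is sound, but it has no slack. The one example with a margin, 18 practices of 10,000 at the higher rate, gives 18 × 10,000 × 0.20 × 0.02 × 0.5 × 0.30 = 108.

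**Step 2: add follow-up.** Children with a 3-month outcome = baseline children × retention. The documents give no retention figure; 70% to 90% is my assumption.

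| Baseline | 70% retained | 90% retained |
|---|---|---|
| 300 | 210 | 270 |
| 100 | 70 | 90 |
| 100, per risk group (÷ 3) | 23.3 | 30.0 |
| 108 | 75.6 | 97.2 |

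The number with both follow-ups, as Section 2.11 asks, cannot exceed these.

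**Step 3: items supported, on the plan's own count of 10 individuals per item.** From 300 at baseline the plan gets 300 ÷ 10 = 30. With an outcome it is 210 ÷ 10 = 21 to 270 ÷ 10 = 27. The final tool in Section 2.6 has 13 numbered questions, some with more than one part, so on this count the 300-child scenario still supports it. The 100-child scenario gives 10 items at baseline and 7 to 9 with an outcome. It is below 13 either way, so that gap comes from the target itself and not from loss.

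**Step 4: participation that would offset the loss.** To end with 300 outcomes from 168 practices, participation would have to be 30% ÷ 0.90 = 33.3% to 30% ÷ 0.70 = 42.9%, rather than 30%.

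**The case against.** The best defence is that 30% is deliberately low. In the back-pain study that Section 2.5 cites, 107 of 244 patients identified (44%) returned the questionnaire and agreed to further contact. At that rate, 168 practices would yield 999.6 × 107/244 = about 438 children, and 300 would remain after about 32% loss. Section 2.11 also plans multiple imputation with a complete-case comparison, and Section 2.5 allows a social-media top-up to at least 300.

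Part of this stands: participation above 30% would create room. But the plan does not present it as an allowance for loss, and at its own worst case there is none. Imputation adds no observed outcomes, and Section 2.11 itself links it to a low percentage of missing data. The top-up also aims at 300 with no term for loss.

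Several stronger readings should be resisted.

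- *That retention is 82%.* Section 2.5 reports that "107 (82%) agreed to further contact". That is consent to contact, not follow-up achieved. Here, consent to be contacted at each follow-up is already part of enrolment (Section 2.13), so applying 82% after baseline (300 × 0.82 = 246) would largely count the same refusals twice.
- *That the 100-child scenario breaks the stated minimum of 100 with the first child lost.* The text ties that minimum to a variance-covariance matrix and does not restrict it to children with outcomes. A matrix of baseline item responses would need only baseline data. Nor does any sentence claim that this scenario meets the minimum.
- *That fewer than 300 leaves the tool unsupported.* The 300 belongs to a ceiling of 30 items. Step 3 shows that 210 to 270 covers 13 questions on the plan's count.

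**Conclusion.** The concern holds as an unstated assumption, not as a calculation error. The scenarios in Section 2.5 deliver 300 or 100 children at enrolment, and the number available for the primary outcome will be lower with any loss at all. That direction needs no assumption beyond the plan's own 30% participation. The size does: over an assumed 70% to 90% retention, 300 becomes 210 to 270 and 100 becomes 70 to 90. The risk groups then hold about 23 to 30 children each, so the stated figure of about 30 is reached only at the top of the range.

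The consequence is moderate. On the plan's own count the 300-child scenario still supports the tool as built. What is unsupported is describing the sample as safe and worst-case without saying that this refers to baseline participation alone. Section 2.5 also turns a rule about events into a count of individuals; that is a separate matter, and the figures here follow the plan's conversion without endorsing it.

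**What to change.** In Section 2.5:

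1. State an assumed 3-month follow-up proportion, labelled as an assumption and given with a range (for example 70% to 90%). Do not take it from the 82% who agreed to further contact in the cited study.
2. Give each scenario as two numbers: baseline recruits, and expected children with a 3-month outcome (300 and 210 to 270; 100 and 70 to 90).
3. Limit the worst-case and safe wording to baseline participation.
4. State the risk-group size (about 23 to 30 in the 100-child scenario) and the number of items supported from children with an outcome, noting that the final tool has 13 numbered questions.

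This restates figures in one section. It requires no extra enrolment, practices or procedures. The only cost is that the stated numbers look less favourable.

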2.2. Participants and eligibility criteria

Children and adolescents who consult their general practitioner because of their knee pain (of both traumatic and non-traumatic origin) during a period of recruitment of 6 months (starting in July 2019) are eligible for inclusion.

2.2.1. Inclusion criteria:

- Age between 8 and 19 years old. The age of 8 is considered to be the lowest age for the children to be able to complete a pain questionnaire or a pain chart without adult guidance³⁸ (provided that the questions are properly worded by taking into account the age-related cognitive abilities^{39,40}), and the age of 19 is defined as the upper limit for the period of adolescence by the World Health Organization⁴¹.

2.2.2. Exclusion criteria:

- Age below 8 years old or over 19 years old
- Consultation for musculoskeletal pain only in a body region different from the knee

- Pain originated by different conditions (e.g. cancer, infections)
- Child is vulnerable (e.g. he/she has experienced a recent trauma and the distress may have an impact on the self-report making it not valid)³⁹
- Inability to take part to the study because of inability to understand or comply

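### Section 2.5 assumes without a source that 20% of registered persons are aged 8 to 19; the share looks high, and every practice count scales with it

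*Combined protocol and SAP*

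**What the plan says.** Section 2.5 (Sample size) states that "at least 168 general practices of a medium size of 5000 individuals each will be needed to recruit at least 300 participants at baseline". The chain behind this runs as follows.

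- Population: "the overall target population includes 840.000 persons (168*5000) registered in general practices, which corresponds to 1/7 of the whole Danish population".
- Age share: "approximately 168.000 (20%) will be aged between 8 and 19 years old".
- Consultations: "1,999 (119 per 10,000 registered persons) of these young people will have a consultation for knee pain in one year". Half of these, 999, fall within the six months of baseline recruitment.
- Participation: "These scenarios are calculated on a conservative estimate of 30% study participation rate". This leads to 300 children.

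The same 20% appears in the other scenarios that state a number of 8-19-year-olds: 56,000 of 280,000, 33,000 of 165,000 and 100,000 of 500,000. At the higher prevalence of 200 per 10,000, the section says that "33 general practices of a medium size of 5000 individuals each would be needed" to reach a minimum of 100 children. It also offers 18 practices of 10,000 as an alternative for 100 children. The consultation prevalences carry citations; the age share does not.

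The age band is fixed by section 2.2, which excludes "Age below 8 years old or over 19 years old".

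**The concern.** The expected number of children is proportional to the age share, so one unsourced figure drives all five practice counts. For a band of 12 single years, 20% means 1.67% of the registered population per year of age. If all years of age were equally large, 60 of them would use up the whole population. Over any longer flat span the share is below 20%, and the 168-practice scenario then falls short of 300 at the stated prevalence and participation.

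What is at stake is feasibility: how many practices to enrol, or how many children to expect from a fixed number. The section presents its approach as cautious, but the caution lies in the participation rate. If the age share is too high, some of that margin is already spent when recruitment opens.

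**Working it through.** **Inputs from the plan.** Practices and sizes: 168, 56, 100 and 33 practices of 5,000, and 18 of 10,000 (section 2.5). Age share 0.20. Annual prevalence 0.0119 for the 168- and 56-practice scenarios and 0.02 for the 100- and 33-practice scenarios. I take 0.02 for the 18-practice scenario too, because it follows directly in that paragraph. Recruitment window 0.5 year. Participation 0.30.

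**Formula.** Children = practices × size × share × prevalence × 0.5 × 0.30.

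**Reproducing the plan's figure.** 168 × 5,000 = 840,000. × 0.20 = 168,000. × 0.0119 = 1,999.2 a year. × 0.5 = 999.6. × 0.30 = 299.88, about 300. The plan's chain holds.

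**What 20% implies.** 8 to 19 inclusive is 12 single-year ages, and 12/0.20 = 60 years on a flat profile. On a flat 80-year profile the share would be 12/80 = 15%, so these 12 ages would have to be 0.20/0.15 = 1.33 times average size to make up 20%. In absolute terms, the plan's one-seventh implies 7 × 840,000 = 5.88 million people. 20% of that is 1.176 million, or 98,000 per year of age, which a register lookup can confirm or refute.

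**Sensitivity to the share.** The documents give no age distribution, so the spans below are my assumptions. Apart from the share, each scenario's inputs multiply to a constant:

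- 168 practices: 840,000 × 0.0119 × 0.15 = 1,499.4
- 56 practices: 280,000 × 0.0119 × 0.15 = 499.8
- 100 practices: 500,000 × 0.02 × 0.15 = 1,500
- 33 practices: 165,000 × 0.02 × 0.15 = 495
- 18 practices of 10,000: 180,000 × 0.02 × 0.15 = 540

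(0.15 here is 0.5 × 0.30.) Constant × share gives the expected number of children:

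| Scenario (target) | 20% (plan) | 17.1% (70 y) | 15% (80 y) | 13.3% (90 y) | 12% (100 y) |
|---|---|---|---|---|---|
| 168 × 5,000 (300) | 299.9 | 257 | 225 | 200 | 180 |
| 56 × 5,000 (100) | 100.0 | 86 | 75 | 67 | 60 |
| 100 × 5,000 (300) | 300 | 257 | 225 | 200 | 180 |
| 33 × 5,000 (100) | 99 | 85 | 74 | 66 | 59 |
| 18 × 10,000 (100) | 108 | 93 | 81 | 72 | 65 |

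**Practices needed for 300 at prevalence 0.0119.** 300 / (5,000 × share × 0.0119 × 0.15), rounded up: 197 / 225 / 253 / 281 for the four assumed spans. At a 15% share the other scenarios would need 100/1.33875 = 74.7, so 75 (plan 56); 300/2.25 = 133.3, so 134 (plan 100); 100/2.25 = 44.4, so 45 (plan 33); and 100/4.5 = 22.2, so 23 of 10,000 (plan 18).

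**Participation that would offset the shortfall with 168 practices.** 300 / (840,000 × share × 0.0119 × 0.5) = 35% / 40% / 45% / 50% for the four spans.

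**Slack in the 18-practice scenario.** 100/540 = 18.52%, so it meets its target at any share of about 18.6% or more.

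**The 33-practice scenario on the plan's own inputs.** 495 × 0.20 = 99.0. The exact requirement is 100 / (5,000 × 0.20 × 0.02 × 0.15) = 33.3, so 34 practices. The 168 and 56 counts are also rounded down (exact values 168.07 and 56.02), but there the loss is a small fraction of a child.

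**The case against.** The strongest reply is that nothing has been miscalculated. The chain reproduces, the 20% is applied consistently, and a population with larger young cohorts could have 20% aged 8 to 19. All of that stands. A reader might infer that 168 practices will deliver 225 children and that the 300 is a mistake. The documents do not support this: 15% comes from an assumed flat 80-year profile, and 225 is one value in a range.

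A reader might also infer that the plan's claim to a worst case is false. That label belongs to the 30% participation rate, not to the age share. The plan's own comparator, the adult back pain tool, had 54% of identified patients return the baseline questionnaire. Participation of about 40% would restore 300 at a 15% share, so the margin may absorb the problem, but the plan does not show that it does.

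Nor does every scenario fail as soon as the share drops below 20%; the 18-practice scenario has some slack. The choice of prevalence (119 or 200) moves the counts by a factor of 1.68, more than 20% against 15% does (1.33). Section 2.5 also allows a 100-child target and a possible social media top-up to 300, and section 2.7.1 provides monthly monitoring of each practice. These soften the consequence. The top-up is only a possibility, though, and the plan itself foresees a sensitivity analysis because that sample may differ.

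Finally, a reader might infer that the tool would carry too many items. On the plan's rule of 10 per item, applied to individuals as section 2.5 applies it, even 180 children would cover 18 items, and the final tool has 13 numbered questions. The stricter figure of 20 per variable would give 11 at 225 children and 15 at 300, but the plan reserves it for low-prevalence binary predictors. The consequence for the tool is slight.

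**Conclusion.** The point holds as an unsupported and apparently optimistic planning input, not as an arithmetic error. At the stated prevalence and 30% participation, any flat age span above 60 years puts the 168-practice yield below 300. For assumed spans of 70 to 100 years the shortfall is about 43 to 120 children (300 − 257 to 300 − 180), or 29 to 113 more practices (197 − 168 to 281 − 168). The direction depends on a roughly flat age profile and the size on the assumed span; the documents settle neither. One small shortfall needs no assumption: 33 practices give 99 children on the plan's own inputs. The effect is confined to the recruitment planning figures. The outcome definitions and the analysis are untouched.

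**What to change.** Replace the 20% in section 2.5 with the number of registered 8-19-year-olds on the participating practices' lists or, failing that, the national register share for those ages, and cite the source. Recompute all five scenarios and round practice counts up; if 20% is confirmed, 33 still becomes 34. If the number of practices is already fixed, restate the expected number of children instead, and show how it varies with participation. The cost is one lookup and a recalculation. The drawback is that the stated practice counts will probably become less favourable.
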